1.1.2 Secondary hypotheses

- 1.1.2.1 Subjects randomized to the ALERT specialist arm will have higher ART uptake compared to subjects in the SOC arm.
- 1.1.2.2 Use of detailed assessments at study entry will allow for the identification of covariates associated with poor retention and initiation of ART.
- 1.1.2.3 Use of an ALERT specialist and a structured retention module intervention will modify the impact of covariates on retention and initiation of ART.

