Facilitating patient navigation of the complex health system (System Literacy) (27) allows better use of available resources, improves communication and can sustain HIV care over time (engagement). One study in 333 HIV-infected found that 71% of the patients needed at least one support service that was ostensibly available to them through their clinic. Services were not accessed due to lack of information (47%) or other logistical barriers (33%; such as confusing instructions or long waiting lists for services) (28). Similarly, in the UC San Diego Health Systems HIV retention project (29), system navigation was frequently cited as the reason for lack of retention.

Finally, people with HIV report fear of disclosure of their diagnosis and potential stigma as significant barriers to care (13, 30), and to accessing social support networks (31). Behavioral models identify stigma and lack of social support as important factors in an individual's risk for poor engagement, particularly within vulnerable populations (11, 32). Qualitative studies also identify stigma and family support as key factors in patients' ability to engage in HIV care (33), and studies have demonstrated associations between lack of HIV disclosure to support networks and poorer psychosocial, adherence, immunologic, and virologic outcomes (31, 32, 34) (34-38). Furthermore, minority patients are more likely to have concerns about stigma and are more likely to change clinics (30, 39) which may contribute to disparities seen in HIV outcomes in minority patients (40, 41).

We hypothesize that an ALERT specialist, who has access to a tracking database, outreach activity, and a structured behavioral intervention to address the above retention barriers, will improve successful continuity of care and ART initiation.

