It is expected that subjects new or returning to care will have regular primary care visits at least 3-4 times in the first year. The ALERT specialist will use the clinic medical record system to abstract data on clinic visits, ART medications, serial HIV RNA and CD4 values, routine CBC and chemistry values, HIV-related and AIDS diagnoses and other medical diagnoses. Data will be entered into the study electronic database. Abstraction will be done at least quarterly for each subject. The ALERT specialist will track the status of each subject and record retention and outreach in the study database. Using data abstracted from the primary care clinic medical records system, the ALERT specialist will record all visits with a prescribing HIV provider, which will document retention as related to the primary study endpoint. For patients in the SOC arm, contact information will be collected for use in the event that the person meets the primary endpoint. Subjects in either arm who reach criteria for the LTFU primary endpoint will be identified by the ALERT specialist. The ALERT specialist will then contact the subject to assure that the patient is not incarcerated or receiving care from an HIV provider at

another facility. Once LTFU is confirmed, the ALERT worker will try to bring the patient in for a primary endpoint visit. All patients will continue to be followed after the primary endpoint (ITT) for assessment of secondary endpoints.

Education Contacts (weeks 1-24). The ALERT specialist will complete a 5 session educational curriculum called a retention module either in person or by phone to the subjects randomized to the ALERT Intervention arm. The 5 retention modules include instruction about the navigation of HIV health systems, HIV literacy, Disclosure, Medication adherence and Continuation with Care, and Self-Efficacy [MOP CCTG 594: 5.0 The 5 Retention Modules for the ALERT specialist]. The goal will be to present the majority of the material within the first 6 months, however scheduling flexibility will be allowed up to the 12 month time-point in order to maximize opportunities for patients to receive the intervention. Subjects that complete all 5 modules will be asked about their reasons motivating them to 1) participate in the study and 2) completing the 5 modules.

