6.3.4 Concomitant Medications

At annual study visits concomitant medications of interest taken since the last visit will be recorded in the source documentation and entered into the concomitant medication log CRF.

6.3.5 *ARV Modifications*

All modifications of ART, including initiation of ART, will be recorded on the CRF's at the 3 month data extractions: including initial doses, patient-initiated interruptions, modifications, and permanent discontinuations. ART will also be reviewed and confirmed at the annual study visits.

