9.6.2 Analysis of Primary Outcome

A survival analysis of "time to LTFU" will be conducted. LTFU is defined as no visit with a prescribing HIV provider in the last 180 days. Time-to-LTFU will be calculated as total days between the first visit and the date when the participant reaches the definition of LTFU.

For example, a subject has his first visit on Jan 1, 2013, and another visit on Mar 1, 2013. If the subject does not have any visits thereafter, or does not have any visits until >180 days later, the subject will be counted as reaching the primary endpoint of LTFU. In this case, the subject would be LTFU if no visit occurred before Aug 27, 2013, (which is 180 days past Mar 1st). The "time-to-LTFU" will be the time period between Jan 1, 2013 and Aug 27, 2013.

At the end of the study, patients who have not reached the primary endpoint will be censored at the time of their last quarterly data extraction.

Patients who meet the primary endpoint and are found to be incarcerated will be removed from the study and censored effective at the time of their incarceration. Those who are incarcerated but return to care upon release, prior to reaching a primary endpoint, will be allowed to remain in study. Patients who change care provider to an external health facility (such as a different clinic system or a nursing facility) will be assessed for their current engagement in care; those who have completed a clinic visit with a prescribing clinician within the 180 days will be considered engaged in

care, and will not be considered LTFU. If possible, these patients will continue to come in for annual study visits.

The null hypothesis is that the median time-to-LTFU estimated using the Kaplan-Meier method will be identical in both groups. The log-rank test will be used to test the null hypothesis against the alternate hypothesis that the median time-to-LTFU is not the same between the groups.

In addition, to assess the factors associated with time-to-LTFU, Cox regression models will be performed on two subgroups, looking at each arm separately. The model will have time to LTFU as the outcome, baseline variables such as demographic, socioeconomic, psychosocial factors, risk behavior, substance use and psychiatric illness as predictors.

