9.6.3 Analysis of Secondary Outcomes

Main Secondary Outcome: The CCTG 594 secondary outcome is time to initiation of ART. A survival analysis of time to initiation of ART will be conducted. Time to initiation of ART will be calculated as total days between the first visit to the ART start date. For those participants who do not start ART, the time to initiation of ART will be censored to the participant's last visit date.

The NULL hypothesis is that the median time to initiation of ART estimated using the Kaplan-Meier method will be identical in both groups. The log-rank test will be used to test the null hypothesis against the alternate hypothesis that the median time to initiation of ART is not the same between the groups.

In addition, to assess the factors associated with time to initiation of ART, Cox regression models will be performed on two subgroups, looking at each arm separately. The model will have time to initiation of ART as the outcome, baseline variables such as demographic, socioeconomic, psychosocial factors, risk behavior, substance use and psychiatric illness as predictors.

9.6.4 Other Secondary Analyses

Descriptive analyses will be conducted for all the secondary analyses including comparisons between randomized groups on the following measures:

- Baseline and follow-up scores on HIV and health literacy assessments, disclosure rates, adherence, and measures of selfefficacy
- Number of primary care visits per year
- HIV RNA < 50 and <200 copies/mL at years 1 and 2
- CD4 cell counts and changes from baseline in CD4 at years 1 through 2
- Scores on Beck Depression Index
- Substance use
- HIV high-risk transmission behaviors
- Time to AIDS diagnosis or death
- Reasons eligible patients decline study participation

For patients who meet the primary endpoint (LTFU) but subsequently return to care, secondary analyses will measure the proportion returning in the intervention vs. SOC arm and the time between their last and return visit with a prescribing provider.

Fisher's exact test will be used for categorical variables; T-test (or Wilcoxon Rank Sum test, if parametric assumptions fail) will be used for continuous variables.

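### Censoring ART non-starters at their last visit loses most of any ALERT effect on ART uptake that works through retention

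*Combined protocol and SAP*

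**What the plan says.** Section 9.6.3 names time to ART initiation as the main secondary outcome, measured from the first visit to the ART start date and compared between arms by log-rank test. Its censoring rule is: "For those participants who do not start ART, the time to initiation of ART will be censored to the participant's last visit date". Last visit is not defined as a prescriber, clinic or study visit.

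Other sections bear on this:

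- Hypothesis 1.1.2.1: "Subjects randomized to the ALERT specialist arm will have higher ART uptake compared to subjects in the SOC arm".
- Section 2.1.2 expects tracking, outreach and coaching together to work on both outcomes: "a structured behavioral intervention to address the above retention barriers, will improve successful continuity of care and ART initiation".
- Section 6.3.5: "All modifications of ART, including initiation of ART, will be recorded on the CRF's at the 3 month data extractions".
- Section 6.2.4: "All patients will continue to be followed after the primary endpoint (ITT) for assessment of secondary endpoints".
- Section 9.6.2, for the primary outcome: "patients who have not reached the primary endpoint will be censored at the time of their last quarterly data extraction".
- Section 9.6.1 sets intention-to-treat as the general principle.

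Section 9.0 gives precedence to a separate SAP, but the documents show no other rule for this outcome. They also contain no fixed-time proportion starting ART and no sensitivity analysis for this censoring.

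**The concern.** The log-rank test needs censoring that is unrelated to the chance of the event. Here the censoring date is when a patient stops attending. A patient out of care is unlikely to start ART, and leaving care is what the intervention is designed to prevent. The censoring is therefore informative, and it differs by arm by design.

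The planned test answers whether patients who are still attending start ART faster under ALERT. The hypothesis asks whether more of those randomized start ART. If ALERT raises uptake by keeping people in care, those extra starts count as events, but they come with matching extra time at risk, and the comparison shows little or nothing. Any effect of the modules on starting ART while in care is kept.

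The result could be a null finding on the main secondary outcome in a trial where ALERT did raise uptake. The Kaplan-Meier curves would also overstate uptake, more so in the arm with more exits.

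**Working it through.** **Inputs from the documents (Section 9.4.1).** 150 per arm, two-sided log-rank at 0.05, 70% (SOC) against 85% (ALERT) free of the endpoint, stated power 87%. Follow-up is at least 48 weeks, or 336 days. LTFU needs 180 days without a visit.

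**The plan's own figure.** HR = ln(0.70)/ln(0.85) = 2.19. Expected events = 150 × (0.30 + 0.15) = 67.5. Freedman power = Φ(√67.5 × 1.195/3.195 − 1.96) = 86.7%, which agrees with 87%. This concerns the primary outcome only; no power is given for ART initiation.

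**Assumptions.** The documents give neither an ART start rate nor a time horizon for 70%/85%. Time to ART in care and time to last visit are taken as exponential, with 50, 70, 80 or 90% in-care uptake by day 336. No one starts while out of care.

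**Base case: retention effect only, no returns.** LTFU by day 336 requires a last visit by day 336 − 180 = 156. So exit by day 156 is set to 30% in SOC and 15% in ALERT. This leaves 0.70^(336/156) = 46% and 0.85^(336/156) = 70% attending at day 336.

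With a and l the cumulative hazards of ART start and exit over 336 days, true uptake is a/(a+l) × (1 − exp(−(a+l))). For 70% in-care uptake, a = 1.204, with l = 0.768 in SOC and 0.350 in ALERT:

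- SOC: 1.204/1.972 × (1 − e^−1.972) = 0.53
- ALERT: 1.204/1.554 × (1 − e^−1.554) = 0.61

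Under last-visit censoring both arms have the same hazard a, so the expected HR is 1. Both Kaplan-Meier curves tend to 70%, which overstates uptake by 17 points in SOC and 9 in ALERT.

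Simulation, 4,000 trials per row:

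| In-care uptake | True uptake, SOC / ALERT | Last-visit rejection | End-of-data rejection |
|---|---|---|---|
| 50% | 36 / 43% | 5.1% | 18.4% |
| 70% | 53 / 61% | 5.1% | 23.6% |
| 80% | 61 / 71% | 5.0% | 28.1% |
| 90% | 72 / 81% | 5.4% | 29.2% |

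The HR is 1.00 with last-visit censoring and 1.21 to 1.22 with end-of-data censoring.

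**Variations.**

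- *Milder exits* (30%/15% leave by day 336): uptake gap 4 to 5 points. Last-visit rejection is about 5%. End-of-data HR is 1.10 to 1.11, with rejection 9 to 13%.
- *Added in-care effect, HR 1.25*: last-visit HR 1.25, power 24 to 40%; end-of-data HR 1.45 to 1.50, power 64 to 82%.
- *Returns*: with 30% of leavers returning, last-visit HR is 1.04 to 1.05. With 60%, it is 1.06 to 1.08 against 1.16 to 1.21 at end of data, so 34 to 49% of the log-HR survives. Runs with 50% returning and slightly different settings gave 26 to 46%.
- *Early ART* (80 or 90% ever start in care, mean 30 or 60 days): uptake gap about 1 to 5 points; end-of-data HR 1.03 to 1.12; last-visit HR still 0.99 to 1.00.
- *Selective loss* (half the patients have twice the ART hazard and half the exit hazard, the rest the reverse): last-visit HR 0.93 to 0.95 while uptake is 6 to 8 points higher with ALERT. A milder log-normal frailty (SD 0.7) gave 0.96 to 0.98, against 1.07 to 1.13 at end of data.

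**The case against.** The main objections concern size and the remedy.

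- *Timing.* If ART starts soon after entry, loss of retention blocks few starts and there is little effect to lose. This stands for the size: 7 to 9 points is not the full range. It does not rescue the rule, because the last-visit HR stays at 1.00.
- *Returns.* Outreach after LTFU runs in both arms (Sections 5.1.4 and 6.2.4) and an endpoint visit is sought (Section 6.2.5), so no returns is the extreme case. This also stands, but at 60% returning about half or more of the log-HR is still lost.
- *Low power after the change.* For a pure retention effect the test would still miss in at least 70% of trials. True; what changes there is mainly the question answered. The gain in power is large when an in-care effect is present as well.
- *Sign reversal.* It needs strong, opposed differences between patients, so it is illustrative only.
- *Undefined term.* Counting study visits would move some censoring dates later, but these too depend on attendance.
- *Ascertainment.* Charts may miss ART started elsewhere. ALERT patients are tracked continuously, while SOC patients are contacted about outside care only on reaching LTFU. Missed starts could therefore be more common in SOC and favour ALERT. This is a real cost of the change and needs reporting.

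A while-in-care comparison is a legitimate question, but the plan does not state it as its question, and hypothesis 1.1.2.1 asks another.

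**Conclusion.** The concern holds. The rule ties censoring to the behaviour that ALERT is meant to change, and it conflicts with the uptake hypothesis, the intention-to-treat principle and the planned follow-up after LTFU. An effect acting only through retention is lost entirely if leavers do not return, and by about half or more if up to 60% do. A mixed effect is understated (HR 1.25 instead of 1.45 to 1.50 in the example).

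The direction follows from the rule itself. The sizes rest on assumed ART start rates, start times, exit timing and return rates, none of which the documents give; the uptake gap at stake ranges from about 1 to 9 points. The primary comparison and its 87% power are unaffected. This should be fixed before analysis because it concerns the named main secondary outcome.

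**What to change.** Replace the censoring sentence in Section 9.6.3 with a rule along these lines: participants who have not started ART are censored at their last quarterly data extraction, whether or not they are still attending. Earlier censoring applies only at withdrawal of consent, incarceration under the existing removal rule, death, or the last verified information for confirmed transfers.

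In addition:

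- Report the proportion of all randomized patients who started ART by week 48, by arm, with death as a competing event.
- Keep last-visit censoring as a sensitivity analysis labelled as while in care, and define last visit.
- Report by arm how many non-starters had unverified ART status, since outside starts may be missed unequally.
- If a separate SAP exists, make the same change there.

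As a separate clarification, state that the time origin is randomization (the baseline study visit) and that patients already on ART at that point are not in the risk set.

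The cost is a short wording change and a few extra table rows. The data are already planned: ART starts are captured at the quarterly extractions, and patients are followed after LTFU. The price is that ART started elsewhere and not visible in the chart counts as not started.

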Ongoing Retention Efforts. The ALERT specialist will continuously monitor visit records on all patients in the ALERT specialist Intervention arm and will utilize all tools developed for clinic specific re-engagement to aggressively track, find, and re-engage patients during the study. Monitoring will include missed visits and intervals between scheduled visits. In addition to continuous monitoring for missed appointments, the ALERT specialist will screen the charts of all enrolled subjects every 3 months to evaluate the number of clinic contacts, missed visits, missed attendance of the retention modules, and any other risks for falling out of care.

Yearly Study Visits. For both arms, a study-specific visit will be conducted at yearly intervals from the enrollment date. The annual visits must occur within a 60 day window before or after the due-date. At the annual study visits the baseline study assessments will be repeated along the collection of plasma which will be stored for future assays. Efforts will be made to have these study visits occur around a regularly scheduled clinic visit.

Though every effort will be made to bring all patients in for annual visits within the 60 day window, subjects may remain in the study if the annual visit is missed (i.e., not completed within the 60 day window).

Compensation. Study participants will be compensated for their time at intake, annual, and endpoint visits which are anticipated to require 1-2 hours for questionnaires and collection of lab specimens.

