6.3.6 Clinical Assessments

Height and Weight

Height and weight should be documented at study entry and weight documented at annual visits.

Treatment-Limiting Toxicity and Diagnoses

The following should be recorded on the CRFs at the annual study visits, and upon reaching the primary endpoint of LTFU (if possible): AIDS-defining events, ART-limiting toxicity, CV events or non-AIDS-related malignancies, STI diagnoses, new medical conditions and death. The source document must include date of diagnosis and date of resolution.

6.3.7 *Immunologic and Virologic Studies*

Nadir CD4+ T-Cell Count

The subject's prior nadir CD4+ cell count (absolute value and date) should be documented during screening and, when possible, a copy of nadir CD4+ cell count report should be included in the source document. If this documentation is not available, then subject recollection will suffice. For

Subjects who do not know the exact nadir value and for whom there is no source documentation, then recall of the categorical nadir (e.g., < 50, < 100, < 200 cells/mm³) will suffice.

CD4/CD8 and HIV-1 RNA

At baseline, at all annual study visits, and upon reaching the primary study endpoint (if possible), a CD4/CD8 count and percentage and HIV-1 RNA will be recorded. The results may be obtained via chart extraction, if available from a CLIA-certified laboratory within 60 days of the study visit. If a result is not available within a 60 day window, it will be drawn at the study visit.

To avoid the need for extra blood draws, efforts will be made, via communication with the Primary Care Provider, to have the patient's routine primary care blood draws occur within the 60 day window of the annual study visits.

6.3.8 Antiretroviral resistance testina

If patients have had an antiretroviral resistance test during routine care, that data will be collected via chart abstraction.

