9.4 Sample Size and Accrual

9.4.1 Power and Sample Size Justification

The primary outcome for this study is to compare the time to LTFU. A secondary outcome is time to initiation of ART. Sample size calculations were based on a two-sided, two-sample log-rank test to compare the differences in time to the-primary endpoint proportions between the intervention arm and the standard of care arm.

Since attrition is a component of the composite endpoint, attrition rates are not used as an adjustment in the power calculations. Assuming 150 subjects per group in each of the two

Table 5: Power based on a two-sided, log-rank test with alpha=0.05 and N=150 per arm (total N = 300)							
Composite	Composite rate	Corresponding	Statistical				
rate without	without	Hazard Ratio	Power (%)				
Endpoint in	Endpoint in	(HR)					
SOC (%)	Intervention						
	(%)						
65	80	1.93	82				
65	85	2.65	97				
70	85	2.19	87				
75	87.5	2.15	78				
75	90	2.73	92				
80	92.5	2.86	87				
80	95	4.35	97				

groups (for a total of 300 subjects), we have 87% power to detect a difference of 15%, assuming a time without a composite endpoint rate of 70% in SOC arm and that the intervention arm will increase the time without an endpoint (to a rate to 85%). This corresponds to a hazard ratio of 2:19. Table 5 shows other possible standard of care rates between arms (and hazard ratios), and corresponding statistical power. The calculations assume that the hazard rates are proportional.

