9.6 Analyses

9.6.1 Statistical Analysis Plan

In general, analyses will incorporate the intent-to-treat principle, namely, all randomized participants will be included in the analysis. The primary analysis compares the ALERT Intervention to the SOC arm. For all secondary analyses of interest, no adjustments for multiple comparisons will be made, and a p-value of 0.05 will be considered statistically significant. Demographic and baseline measurement variables will be summarized via standard descriptive statistics.

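### Section 9.6.4 tests viral suppression with no value assigned to patients who lack an HIV RNA result, although losing the result is tied to the loss to follow-up that ALERT is meant to change

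*Combined protocol and SAP*

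**What the plan says.** Section 9.6.4 introduces its list with "Descriptive analyses will be conducted for all the secondary analyses including comparisons between randomized groups on the following measures". The list includes "HIV RNA < 50 and <200 copies/mL at years 1 and 2", and the section closes by stating that Fisher's "exact test will be used for categorical variables". Section 9.6.1 adds that for secondary analyses, without multiplicity adjustment, "a p-value of 0.05 will be considered statistically significant". The RNA comparison is therefore labelled descriptive but comes with a test and a threshold. Suppression is also a listed secondary objective (1.3.4.3).

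On who is analysed, section 9.6.1 says that, in general, "all randomized participants will be included in the analysis". It does not say what value a participant without an RNA result takes. The time-to-event outcomes do have such rules: time to LTFU is censored at the last quarterly extraction (9.6.2) and time to ART at the last visit (9.6.3).

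On how RNA is obtained, section 6.3.7 accepts a chart result within 60 days of the study visit and otherwise has it drawn at that visit. For patients who become LTFU it is recorded "upon reaching the primary study endpoint (if possible"). Section 6.2.4 says "subjects may remain in the study if the annual visit is missed", and section 6.2.5 makes the endpoint visit depend on the patient's willingness.

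**The concern.** Fisher's test needs a yes or no for every participant counted. With no rule, software drops those without a result, and the comparison becomes one among participants who were measured. Being measured depends largely on attending care, and attending care is the primary outcome. The comparison would then condition on something that the intervention is meant to change, and the protection of randomisation would be lost.

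The usual direction is against ALERT. The SOC arm loses more of its unsuppressed patients from the denominator, so its observed suppression rises more. The trial could then show better retention and apparently no virologic gain, only because of who was counted. The silence also leaves the denominator to be chosen after the data are seen.

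**Working it through.** **The plan's own figure.** Section 9.4.1 gives 87% power for 70% versus 85% free of the endpoint, 150 per arm. HR = ln(0.70)/ln(0.85) = 2.195. Expected events = 150 × 0.30 + 150 × 0.15 = 67.5. Freedman's formula: Φ(√67.5 × 1.195/3.195 − 1.96) = 86.7%. The figure reproduces and is not in dispute. No rate or power is stated for suppression.

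**Inputs.**
- From section 9.4.1: LTFU 30% in SOC and 15% in ALERT, 150 per arm. Table 5 gives no time horizon. Treating these rates as status when RNA is due is an assumption.
- Assumed, not in the documents: suppression 75% if retained and 10% if LTFU; a result for 95% of retained and 20% of LTFU patients, the same in both arms.

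**True suppression.**
- SOC: 0.70 × 0.75 + 0.30 × 0.10 = 55.5%
- ALERT: 0.85 × 0.75 + 0.15 × 0.10 = 65.25%
- Difference: 9.75, or 9.8 points

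**Available results only.**
- SOC: (0.70 × 0.95 × 0.75 + 0.30 × 0.20 × 0.10)/(0.70 × 0.95 + 0.30 × 0.20) = 0.50475/0.725 = 69.6%
- ALERT: (0.85 × 0.95 × 0.75 + 0.15 × 0.20 × 0.10)/(0.85 × 0.95 + 0.15 × 0.20) = 0.608625/0.8375 = 72.7%
- Difference: 3.1 points; Fisher power about 7%

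**All randomised, no result = not suppressed.** The numerators above over everyone: 50.5% versus 60.9%, a difference of 10.4 points; power about 41%. With complete data the power would be about 37%, so the comparison is weak under any rule.

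**If more LTFU patients are measured** (other inputs unchanged; true difference 9.8):

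| LTFU patients with a result | Available-results difference |
|---|---|
| 20% | 3.1 |
| 40% | 5.4 |
| 60% | 7.3 |

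**If more LTFU patients are suppressed** (20% of them measured):

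| Suppressed if LTFU | True difference | No result = not suppressed |
|---|---|---|
| 10% | 9.8 | 10.4 |
| 40% | 5.3 | 9.5 |
| 60% | 2.2 | 8.9 |
| 75% | 0 | 8.4 |

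In the last row there is no virologic effect, yet Fisher's test rejects about 28% of the time, because the rule then measures who was tested.

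**The sign is not fixed.** Suppose no LTFU patient has a result or is suppressed, all retained patients are measured, and the extra 15% whom ALERT retains are suppressed at 50% against 80% in the others. Available results give ALERT (0.70 × 0.80 + 0.15 × 0.50)/0.85 = 74.7% against 80% for SOC. Over all randomised it is 63.5% against 56%, or 7.5 points in favour of ALERT.

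**The case against.** A reader might infer that patients who fall out of care will have no RNA result. The documents do not support that. Charts are abstracted at least quarterly, follow-up continues after LTFU for secondary endpoints, outreach is made in both arms, an endpoint visit is attempted, and RNA is drawn if the chart has none (5.1.4, 6.2.4, 6.2.5, 6.3.7). LTFU is also a first gap of more than 180 days, and section 9.6.4 expects some patients to return. These routes reduce the missingness, but each still depends on attendance.

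A reader might also infer that the plan calls for a test on available results. It does not say so. Section 9.6.1 states the intention-to-treat principle, and section 9.0 defers to an SAP that takes precedence, of which no detail beyond section 9 is in the text reviewed. If the rule is there, a cross-reference is enough. As the text stands, the principle says who is included and not what value they take.

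Nor do the documents make suppression the main evidence that retention improves health. The main secondary outcome is time to ART initiation, and RNA is one of nine items under other secondary analyses.

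The strongest objection is to the obvious remedy. Counting no result as not suppressed can manufacture a benefit, as the last table shows, and would score participants withdrawn under section 8.1 as virologic failures. That stands, so the rule cannot be used alone.

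**Conclusion.** The gap is real and worth closing, at the level of a recommendation. The plan attaches a test to a binary outcome whose missingness is likely to follow the primary outcome, and gives no value to those without a result. On available results the arm difference would tend to be understated: 3.1 points against 9.8 in the main illustration, and 5.4 or 7.3 if 40% or 60% of LTFU patients are measured. The size rests on assumed suppression and availability rates and on reading Table 5's LTFU rates as status at the RNA time point. If LTFU patients were suppressed as often as retained ones, available results would not be biased and the alternative rule would be.

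A reader might conclude that the benefit would be wholly hidden. That happens only in the extreme case where no LTFU patient has a result and suppression among retained patients is equal in the two arms. The primary analysis is not affected.

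**What to change.** In section 9.6.4:

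1. Define suppression at years 1 and 2 over all randomised participants whose ±60-day window has closed within their planned follow-up. Enrolment and study-closure dates should decide this, not attendance. The 48-week minimum is day 336, inside the year 1 window (365 ± 60, days 305 to 425), and late enrollees may have no year 2 time point. Neither group should be counted as failures.
2. Use the value nearest the due date, including outside-provider results, and count no result as not suppressed. Section 6.1 anchors the window to the due date and section 6.3.7 to the study visit; the due date still works when the visit is missed.
3. State how participants withdrawn under section 8.1, such as for pregnancy or incarceration, enter the analysis, instead of scoring them automatically as failures.
4. Compare arms stratified by site and new/returning status, for example by Cochran-Mantel-Haenszel.
5. Report missingness by arm and reason.
6. Bracket the result with multiple imputation and the available-results analysis, and do not claim a virologic benefit that appears only when missing is counted as not suppressed.
7. Describe the comparison as secondary and unpowered.

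The cost is wording and some programming, with no new visits or blood draws. Two limits remain: the latest enrollees leave the year 1 denominator, and a suppressed patient in care elsewhere whose result cannot be obtained counts as not suppressed in the main analysis.
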